Run-in Period: After meeting Screening eligibility criteria, patients will enter a 2-week single-blind Run-in Period. On day 1 of the Run-in Period patients will be dispensed 4 tablets of singleblind placebo to be administered at the site. For the remainder of the Run-in Period, patients will take a single tablet of study drug every morning. Each evening patients will rate and record the intensity of their DPNP over the previous 24 hours based on Question 5 of the BPI-DPN by answering the question "Please rate your pain due to your diabetes by indicating the one number that best describes your pain on the average." (0 [no pain] to 10 [pain as bad as you can imagine]) in their daily pain diary and will rate the interference of pain with sleep by completing Question 9F of the BPI-DPN. The ADPS will be calculated using all available daily pain diary data. This derived value of the ADPS over Week 2 will serve as the Baseline measure used for analyses. In order to qualify for randomization, patients must have completed ≥70% of the daily pain diary entries during the second week of the Run-in Phase, meet criteria for moderate to severe pain, and demonstrate ≥80% compliance with taking the expected amount of placebo tablets during the Run-in Period. During the Run-in Period patients will not be allowed use of any rescue medication. On the morning of the Run-in Visit, patients may eat a light meal prior to the visit.

Note: Patients who fail Screening may be rescreened ONCE after discussion with the Medical Monitor. Patients who begin the Screening period prior to this amendment and who otherwise would qualify for the study may be rescreened again so as to allow them to begin the Run-in Phase following implementation of this amendment.

Randomization/Double blind Treatment Period: Patients who successfully complete the 2-week single-blind placebo Run-in Period and meet all other eligibility criteria will enter a 6-week double-blind Treatment Period.

Patients will be randomly assigned in a 1:1:1 ratio among the following 3 treatment groups:

- **Group 1:** LX9211 100 mg* / 10 mg**, once daily (qd)
- **Group 2:** LX9211 200 mg* / 20 mg**, qd
- Group 3: Placebo, qd
- * Loading dose (Day 1)

** Maintenance dose (Day 2 – Week 6 Visit)

Implementation of the treatment randomization schedule will be centralized. A 1:1:1 ratio for assigning patients among the treatment groups will be accomplished by use of randomly permuted blocks of fixed size.

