7.6.1 Primary Efficacy Analysis

The primary endpoint is the change from Baseline to Week 6 in ADPS, based on Question 5 of the BPI-DPN, the 11-point scale (0 [no pain] to 10 [pain as bad as you can imagine]). The primary analysis will be based on observed data including data measured after the initiation of rescue medications.

Baseline is defined as the average of the Week 2 Run-in Period data collected by patients in the daily pain diary, provided that ≥ 5 days from that period are available for analysis. The post-Baseline values will be calculated by week as the mean value of the Question 5 for ADPS of the BPI-DPN, rated by patients each evening and collected during the target week period. A minimum of 4 non-missing data within the target week period is required for the calculation. The change from

Baseline values at post-Baseline weeks will be calculated as the absolute difference between the Baseline value and post-Baseline values, ie

$$\text{change from Baseline} = \text{post-Baseline value} - \text{Baseline value}$$

The ADPS calculated for each post-Baseline week until Week 6, and the change from Baseline in ADPS at post-Baseline weeks until Week 6 will be summarized by Week using standard descriptive statistics. Data from all study visits, scheduled and unscheduled, and from the daily pain diary will be listed.

A restricted maximum likelihood-based, MMRM approach will be used to assess the difference between LX9211 and placebo in the primary endpoint (ie, change from Baseline to Week 6 in the ADPS derived from data collected daily from Question 5 of the BPI-DPN instrument). The MMRM model will include fixed effects of treatment, week, treatment-by-week interaction, the randomization stratum of Baseline pain severity (moderate, severe), and Baseline ADPS score as a covariate. An unstructured covariance structure will be used to model the within-patient error. Other covariance structures will be explored should convergence not be met. The Kenward-Roger approximation will be used to estimate the denominator degrees of freedom.

The adjusted mean change in ADPS from baseline to Week 6 for each treatment group and the 95% confidence intervals (CIs) will be estimated in the framework of this model, as well as the between-group differences (comparing each LX9211 treatment group to placebo) and the 95% CIs for the difference.

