7.6.2 Secondary Efficacy Analysis

Analysis of the secondary efficacy endpoints will be based on the mITT population. Descriptive statistics for all the secondary efficacy endpoints will be presented by treatment group and by study visit/week where appropriate. Data from all study

visits, scheduled and unscheduled, and from the daily pain diary will be listed. Post-Baseline data through Week 6 will be used in the analyses where inferential statistics are presented, including observations occurring after discontinuation of study drug. Figures displaying mean change from Baseline, LS mean change at Week 6, and bar charts displaying proportions, will be presented by treatment group.

Continuous secondary efficacy endpoints: BPI-DPN scores, measured at multiple time points, will be analyzed using a similar modeling strategy as for the primary endpoint.

The ordinal secondary endpoint, PGIC response at Week 6, will be analyzed using an analysis of variance (ANOVA) model to test and estimate the treatment effect.

Categorical secondary endpoints: the proportion of responders based on Question 5 of BPI-DPN and the proportion of patients discontinuing study treatment due to lack of efficacy will be compared between treatments using a Cochran-Mantel-Haenszel (CMH) test stratified by the randomization factor of Baseline pain severity (moderate, severe). Patients with missing measurement at Week 6 will be considered non-responders. In general, a non-responder imputation (NRI) rule will be applied to assign outcomes to all study weeks with missing observations.

The Kaplan-Meier (KM) method will be used to generate statistical summaries of the time to loss of efficacy variable among patients who achieve $\geq 30\%$ reduction in ADPS based on Question 5 of the BPI-DPN from Week 6 to Week 11.

The qualitative patient interview substudy will be managed by a separate vendor (RTI-Health Solutions, Research Triangle Park, NC). The data analysis methods they employ will be detailed in a separate statistical analysis plan and the results will be reported separately by them.

7.6.2.1 Proportion of patients with $\geq 30\%$ reduction in pain intensity in ADPS based on Question 5 of the BPI-DPN from Baseline to Week 6

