The change from Baseline to Week 6 in pain severity and pain interference will be summarized using standard descriptive statistics and the treatment effect will be evaluated using a similar MMRM method as specified for the primary efficacy analysis of change from Baseline to Week 6 in ADPS where the time point will be

CONFIDENTIAL

substituted by Visit instead of Week. The Baseline covariate included in the model is the Baseline value of the dependent variable under analysis.

In addition, the change from Baseline to Week 6 in pain interference with sleep based on Question 9F, rated by patients and collected each evening in the daily pain diary will be summarized using standard descriptive statistics and the treatment effect will be evaluated using a similar MMRM method as specified for the primary efficacy analysis of change from Baseline to Week 6 in ADPS. In this case, the Baseline value for the interference with sleep using Question 9F of the BPI-DPN is defined as the value collected at the time of the clinic visit on Day 1. The post-Baseline values will be calculated by week as the mean value of the Question 9F of the BPI-DPN, rated by patients each evening and collected during the acceptable week period. A minimum of 4 non-missing data within the target week period is required for the calculation.

7.6.2.4 Proportion of patients discontinuing treatment due to lack of efficacy based on data collected for Question 5 of the BPI-DPN

This endpoint will be derived as follows:

1. Condition on the eCRF item if the patient stopped study treatment with reason of Lack of Efficacy.
2. If "Yes" to the above, calculate the % change from Baseline of ADPS based on Question 5 of the BPI-DPN during the double-blind Treatment Period, starting at Baseline and ending on the last assessment before the patient stopped study treatment. No minimum number of assessments is required.
3. If the derived value in #2 $\geq 30\%$, then the patient is classified as a "responder". If otherwise (including all mITT patients), then the patient is classified as a "non-responder".

Where % change from Baseline = $100 * (\text{last week of treatment value} - \text{Baseline value}) / \text{Baseline value}$.

The frequency and percentage of patients discontinuing treatment during the double-blind Treatment Period due to lack of efficacy will be presented by treatment group. Similarly, this endpoint will be analyzed as described in for [Section 7.6.2.1](#).

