7.6.2.5 Patient Global Impression of Change (PGIC) at Week 6

The PGIC, a 7-point rating scale, will assess the patient's belief about their overall improvement experienced at the end of treatment.

The frequency and percentages of patients within each category at Week 6 will be presented by treatment group. The treatment effect will be evaluated using an

ANOVA model with treatment and randomization stratum of Baseline pain severity (moderate, severe) as independent variables. Least-square means of PGIC in each treatment group and the difference between LX9211 and placebo for each comparison, along with their 95% CIs and p-value will be presented.

7.6.2.6 Time to loss of efficacy from Week 6 to Week 11 among patients achieving $\geq 30\%$ reduction in pain intensity in ADPS based on Question 5 of the BPI-DPN at Week 6

Time to loss of efficacy is defined as the time from the date of Week 6 visit to the date of termination of safety follow-up due to lack of efficacy. Termination of safety follow-up due to other reasons and death are competing risk. Patients who have terminated the safety follow-up due to any reason other than lack of efficacy after Week 6 visit or have completed the study through Week 11 will be censored at the date of the last ADPS assessment based on Question 5 of the BPI-DPN collected by patients in the daily pain dairy.

Time to loss of efficacy (weeks) = (date of termination of safety follow-up due to lack of efficacy or censoring – date of Week 6 visit + 1) / 7.

Only patients who achieved $\geq 30\%$ reduction in pain intensity in ADPS based on Question 5 of the BPI-DPN from Baseline to Week 6 will be included in the analysis of time to loss of efficacy.

Kaplan-Meier estimates and the associated 95% CIs of the median, 25th, and 75th percentile will be presented. The 2-sided 95% CIs will be computed using the log-log transformation.

The minimum and maximum time to loss of efficacy (using censored and event times) will also be presented.

The survivor function will be displayed graphically by treatment group using a KM curve.

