7.6.5.1 Change from Baseline to Week 6 in the NPSI

The NPSI, a 12-item questionnaire, assesses the different components of neuropathic pain syndromes (ie, spontaneous ongoing and paroxysmal pain, evoked pain, paresthesia/dysesthesia). 10-items related to different pain descriptors (eg, burning, squeezing, electric-shock, stabbing, tingling) allows assessment of the different dimensions of neuropathic pain and 2 items on frequency and duration of pain.

The total intensity score and the 5 subscores (burning spontaneous pain, pressing spontaneous pain, paroxysmal pain, evoked pain, and paresthesia/dysesthesia) will be calculated as:

- Total intensity score: $Q1+Q2+Q3+Q5+Q6+Q8+Q9+Q10+Q11+Q12$
- (Superficial spontaneous) Burning pain: $Q1$
- (Deep spontaneous) Pressing pain: $(Q2+Q3)/2$
- Paroxysmal pain: $(Q5+Q6)/2$
- Evoked pain: $(Q8+Q9+Q10)/3$
- Paresthesia/dysesthesia: $(Q11+Q12)/2$

Baseline will be the data collected on Day 1 at Visit 3. The change from Baseline to Week 6 in total intensity score and the 5 subscores will be summarized using standard descriptive statistics and the treatment effect will be evaluated using an ANCOVA model fitted for the fixed effects of treatment, the randomization stratum of Baseline pain severity (moderate, severe), and the continuous fixed covariate of Baseline score. The ANCOVA analysis will be performed at Week 6 only.

The adjusted mean change from Baseline to Week 6 for each treatment group and the 95% CIs will be estimated in the framework of this model, as well as the between-group differences (comparing each LX9211 treatment group to placebo) and the 95% CIs for the difference.

Summarization of the inferential statistics will include the LS means, SE of the estimates, p-values, and 2-sided 95% CIs. These statistics will be provided for the

CONFIDENTIAL

Document Date: 07JUN2022

Page 34 of 55

ST-AD-008 version 05

within treatment group changes from Baseline and for the comparison of LX9211 versus placebo for the change from Baseline scores. Tabulation of the inferential results (CIs and p-values) will include the observed model findings.

7.6.5.2 Change in Question 5 of the BPI-DPN from Baseline to each post-Baseline visit

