Appendix 4: Patient Global Impression of Change (PGIC)

PATIENT GLOBAL IMPRESSION OF CHANGE (PGIC)

Since the start of the study, my overall status is:

✓ one box only:

- [1] Very Much Improved
- [2] Much Improved
- [3] Minimally Improved
- [4] No Change
- [5] Minimally Worse
- [6] Much Worse
- [7] Very Much Worse

(US/English)

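### PGIC at Week 6 is adjusted only for the two-level pain-severity stratum; adding continuous Baseline ADPS, which is measured before randomisation, might gain a little precision at almost no cost

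*SAP*

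**What the plan says.** SAP 7.6.2 gives the general method for PGIC: "The ordinal secondary endpoint, PGIC response at Week 6, will be analyzed using an analysis of variance (ANOVA) model to test and estimate the treatment" (the last word of the sentence is left off here). SAP 7.6.2.5 names the terms, an "ANOVA model with treatment and randomization stratum of Baseline pain severity (moderate, severe) as independent variables", and asks for least-squares means, the difference from placebo for each dose, 95% confidence intervals and p-values. No continuous covariate appears in either place.

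The neighbouring linear models are built as follows.

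- Primary MMRM (SAP 7.6.1): treatment, week and their interaction, then "the randomization stratum of Baseline pain severity (moderate, severe), and Baseline ADPS score as a covariate".
- BPI-DPN items (SAP 7.6.2.3): "The Baseline covariate included in the model is the Baseline value of the dependent variable under analysis".
- NPSI ANCOVA (SAP 7.6.5.1): treatment, stratum and "the continuous fixed covariate of Baseline score".

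On Baseline ADPS, the Run-in text of the protocol synopsis says: "This derived value of the ADPS over Week 2 will serve as the Baseline measure used for analyses". SAP 6.1.1 requires at least 5 diary days to compute it. The stratum (SAP 7.2) comes from the same diary item, averaged over both Run-in weeks, rounded and split into 5-7 and 8-9. The PGIC item (SAP Appendix 4) reads: "Since the start of the study, my overall status is".

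**The concern.** Baseline pain is a plausible predictor of how patients in a pain trial rate their overall change. The planned PGIC model sees it only as moderate or severe. The moderate class alone takes in rounded averages of 5, 6 and 7, so any baseline pain variation within a class that predicts PGIC stays in the residual. In the primary model the SAP does not rely on the stratum alone, since it uses the stratum and Baseline ADPS together.

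At stake is the width of the interval for a listed secondary endpoint at each dose. In a linear model, adding a prognostic pre-randomisation covariate leaves the target, a difference in mean PGIC, unchanged and can reduce its standard error.

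**Working it through.** **The plan's own figures.** The documents give no standard deviation, power or precision target for PGIC. The only sizing is for the primary endpoint (Protocol 10.1, SAP 2.3): difference 1, SD 2, two-sided Dunnett at 0.05, 75 completers per arm, 80% power. It reproduces. The simulated Dunnett critical value with 222 degrees of freedom is 2.225. Power is 0.798 for one comparison, and 0.807 for at least one when only one dose works. Then 75/(1 - 0.20) = 93.75, rounded up to 94, and 3 x 94 = 282. I take 75 per arm as the number with a Week 6 PGIC, which is an assumption.

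**Availability of the covariate.** Entry needs at least 70% of diary entries in the second Run-in week (Protocol 6.1, criterion 10). Since 0.70 x 7 = 4.9, that means 5 of 7 days, which is the minimum for computing Baseline ADPS. Adding the term should lose almost nobody.

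**Effect on the standard error.** Let r be the correlation of Baseline ADPS with PGIC within strata. The planned model has 4 parameters, so its residual df is 225 - 4 = 221, or 220 with the covariate. The ratio of the new to the planned standard error is approximately

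sqrt[ (1 - r²) x df/(df - 1) x (1 + 1/(df - 1)) ], with df = 221.

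The last two factors are the lost degree of freedom and the expected cost of chance imbalance in the covariate. Together they are (221/220)² = 1.0091.

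| assumed r | calculation | SE ratio | equivalent n per arm (75/ratio²) |
|---|---|---|---|
| 0 | sqrt(1.00 x 1.0091) | 1.005 | 74.3 |
| 0.1 | sqrt(0.99 x 1.0091) | 1.000 | 75.1 |
| 0.2 | sqrt(0.96 x 1.0091) | 0.984 | 77.4 |
| 0.3 | sqrt(0.91 x 1.0091) | 0.958 | 81.7 |

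Break-even is at 1 - r² = 1/1.0091, so r is about 0.1.

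**What the stratum already absorbs.** The relevant r is what remains after the stratum. I simulated Run-in means as normal with mean 6.5 to 7 and SD 1.0 to 1.2, and weekly noise of SD 0.5. All of these are assumptions. The stratum then explains 44 to 57% of the variance of Baseline ADPS. Overall correlations of 0.1, 0.2 and 0.3 leave within-stratum correlations of about 0.07, 0.14 and 0.20 to 0.23. The standard error falls by about 0.3%, 1% and 2 to 3%, before the fixed cost of about 0.5%.

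**The case against.** A reader might infer that the SAP is inconsistent, since its other linear efficacy models carry a continuous baseline. The documents do not support that. Those models use the baseline of their own outcome: ADPS for ADPS, the item's own value for BPI-DPN, the NPSI score for NPSI. PGIC has none. The ADPS responder and lack-of-efficacy endpoints also adjust for the stratum alone, and so does the test for PGIC in Protocol 10.4.2.2. This part of the objection stands in full.

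A reader might also infer that the comparison is biased, or that chance imbalance within a stratum is a fault. Neither follows. Omitting a prognostic covariate from a randomised linear comparison causes no bias and no type I error inflation, and the planned interval already allows for chance imbalance. Secondary endpoints are, besides, unadjusted for multiplicity and declared exploratory (SAP 7.6).

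Lastly, a loss of precision cannot be stated as fact. PGIC is a global rating of change, its correlation with baseline pain could be near zero, and nothing in the documents favours 0.2 or 0.3 over 0. That stands too.

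What the objection does not do is count against the change. A covariate need not be the outcome's own baseline. It need only be measured before randomisation and plausibly prognostic. The SAP neither rules out Baseline ADPS for PGIC nor gives a reason for leaving it out.

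**Conclusion.** The planned PGIC model is valid. Adding Baseline ADPS is an optional refinement with a small, conditional gain: from about 0.5% worse in standard error at r = 0 to about 4% better at r = 0.3, with 0 to 3% realistic once the stratum's share is counted. A gain above 5% would need a within-stratum correlation above roughly 0.3. These figures rest on 75 evaluable patients per arm, a linear relation, and assumed correlations and Run-in distributions. The case for acting is the low cost and the asymmetry between a bounded loss and a possible gain of a few percent.

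**What to change.** Before unblinding, change the PGIC sentence in SAP 7.6.2 and the model statement in SAP 7.6.2.5 to an ANCOVA with treatment, randomisation stratum of baseline pain severity, and Baseline ADPS (the Week 2 Run-in mean of SAP 6.1.1) as a continuous covariate. Use it for the least-squares means, differences, intervals and p-values. The cost is SAP wording, one model term and one degree of freedom. No new data are needed.

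Separately, Protocol 10.4.2.2 plans a stratified Cochran-Mantel-Haenszel test for PGIC, whereas the SAP uses ANOVA, and SAP Section 8 does not list that change. The same edit could record it.

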5.1 Overall Study Design

This is a Phase 2, multicenter, randomized, double-blind, placebo-controlled, parallel-group study in patients with DPNP.

Scheduled study visits in the clinic will occur during Screening; at the initiation of the 2-week single-blind placebo Run-in Period; on Day 1 (Baseline) and during Weeks 2, 4, and 6 of the double-blind Treatment Period, and at Week 11 (Week 5 of the single-blind Safety Follow-up Period).

[figure not shown]
Male and female patients of nonchildbearing potential, age 18 years and above, diagnosed with T1DM or T2DM and with chronic DPNP, and who meet all inclusion and no exclusion criteria are eligible for enrollment.

Eligible patients may continue use of medications prescribed for DPNP including pregabalin, gabapentin, and antidepressant medications, as long as they have been at stable doses for at least 1 month prior to Screening and are willing to maintain their doses for the duration of the study. Use of any opioid medications for the management of DPNP within the 2 months prior to Screening is not permitted.

The treatment schema is summarized in Figure 5.1-1.

Figure 5.1–1 Treatment Schema

R = randomization EOT = end of treatment EW = early withdrawal

- ** Maintenance Dose (Day 2 Week 11 Visit)
- @ Day 1 may occur up to 2 weeks plus 3 days after start of the Run-In period

2 Optional Substudies:

- PK Evaluation and possible biomarker analysis (up to 30 patients) —
 Days 1 and 2, Week 2, Week 4, Week 6 or EOT/EW, Week 11 or 35 Days after
 EOT/EW
- Exit Phone Interview Within 2 to 3 weeks following the Week 6 Visit or EOT/EW

^{*-} Loading Dose (Day 1)

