7.2 Patient Disposition and Data Sets Analyzed

Patient disposition will be listed and summarized by treatment group and overall, and will include the number and percentage of patients:

- Screened
- Entered single-blind placebo Run-in Period
- Discontinued single-blind placebo Run-in Period
- Randomized
- Randomized and not treated
- Treated
- Completed double-blind Treatment Period
- Discontinued double-blind Treatment Period
- Entered optional PK substudy
- Entered optional qualitative patient interview substudy
- Completed single-blind placebo Safety Follow-up Period
- Discontinued single-blind placebo Safety Follow-up Period

CONFIDENTIAL

Document Date: 07JUN2022

Page 23 of 55
ST-AD-008 version 05

- Included in each study population (ITT, mITT, PP, PK – Substudy, PK - C_{trough} and Safety)

The number and percentage of patients who complete the study and who discontinue early (including a breakdown of the primary reasons for discontinuation), will be presented for the ITT population. In addition, the number of patients who discontinue from the double-blind Treatment Period and single-blind Safety Follow-up Period will be summarized by treatment group, respectively.

A summary of patient enrollment by site will also be provided by treatment group and overall for the ITT population. A summary of patient enrollment by randomization strata of baseline pain severity (moderate or severe pain, based on ADPS) will also be provided by treatment group, respectively.

Randomization strata will be collected in the Interactive Voice/Web Response System (IXRS) and it is defined as the average of the scores recorded in the pain diary, ie, Question 5 of the BPI-DPN, during the 2-week single-blind Run-in Period. The rounded average score will be classified as below:

- Moderate: [5-7]
- Severe: [8-9]

A summary of the reasons for screen failure as well as the number of patients screened but not randomized will be produced. No other information for screen failures will be presented.

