7.6.3 Sensitivity Analysis

In the event that rescue medication is used, a supplementary MMRM model will be applied to the primary endpoint dataset that excludes data collected after the initiation of the rescue medication using the mITT population. This model will be parameterized in the same manner as will be used for the primary analysis of this endpoint.

In addition, to assess the robustness of the MMRM analyses performed under the MAR assumption, and given the long half-life of LX9211, PMMs with copy reference-based imputation methods will be applied on both datasets (with and without data collected after the initiation of the rescue medication) using the mITT population.

CONFIDENTIAL

Document Date: 07JUN2022

Page 32 of 55

ST-AD-008 version 05

Methods will be adopted to estimate for both non-monotone and monotone missing data patterns. Imputations for the non-monotone missing data pattern will be the initial step. The imputation algorithm based on Monte Carlo Markov Chain methodology will be used assuming a MAR mechanism for the missing data; 100 imputations will be used. Then multiple imputations will be performed to assign the response variable at consecutive study weeks in a sequential manner for the monotone missing data pattern. For this chain-based method, control-based imputation will be applied so that there is no direct use of observed data from the LX9211 treatment groups in estimating the imputation model. The method is derived such that it builds its imputation only on the placebo group data. The imputed datasets will be combined by use of Rubin's rule and analyzed using an analysis of covariance (ANCOVA) model fitted for the fixed effects of treatment, the randomization stratum of the Baseline pain severity (moderate, severe), and the continuous fixed covariate of Baseline score. The ANCOVA analysis will be performed at Week 6 only. Summary statistics from applying the ANCOVA model across the multiple imputed datasets will be combined to obtain an overall estimate of the treatment group differences.

Sensitivity analyses are not planned for analyses of the secondary or other efficacy endpoints.

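### SAP 7.6.2.6 calls its endpoint time to loss of efficacy but counts only departures from follow-up for lack of efficacy, so a Week 6 responder whose pain returns and who stays to Week 11 is event-free

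*SAP*

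**What the plan says.** **Entry and event.** SAP 7.6.2.6 restricts the analysis to patients with at least a 30% ADPS reduction from Baseline at Week 6. The time measured is "the time from the date of Week 6 visit to the date of termination of safety follow-up due to lack of efficacy".

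**Censoring.** Patients who leave for any other reason, and those who "have completed the study through Week 11 will be censored at the date of the last ADPS assessment", contribute no event. The same section also says "Termination of safety follow-up due to other reasons and death are competing risk", yet it censors those terminations and uses ordinary Kaplan-Meier estimates.

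**Protocol.** Sections 10.3.2 and 10.4.2.2 name the endpoint and the Kaplan-Meier method. Neither defines the event.

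**The neighbouring endpoint.** For discontinuation due to lack of efficacy, SAP 7.6.2.4 begins "Condition on the eCRF item if the patient stopped study treatment with reason of Lack of Efficacy". It then requires the analyst to "calculate the % change from Baseline of ADPS based on Question 5 of the BPI-DPN during the double-blind Treatment Period" and classifies the patient on a 30% increase.

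**Follow-up conditions.** All arms take placebo after Week 6 (Protocol synopsis, Duration of Treatment; SAP 7.2 lists "Completed single-blind placebo Safety Follow-up Period"). Rescue acetaminophen is allowed (Protocol 5.1.4). After Week 6 the only scheduled clinic visit is the last one: "and at Week 11 (Week 5 of the single-blind Safety Follow-up Period". Daily Question 5 ratings continue to the end of follow-up (Protocol 8.1.4).

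**Status.** SAP 7.6 makes the secondary endpoints exploratory. SAP 7.6.3 adds: "Sensitivity analyses are not planned for analyses of the secondary or other efficacy endpoints".

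**The concern.** Patients enter this analysis on a pain score, but a pain score cannot take them out of it. ADPS selects the responders and dates the censoring; it never marks a loss. A reader of a curve with this title would take the event-free share to be the patients who still have their pain relief. It is in fact the patients who have not left follow-up for lack of efficacy.

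The setting allows the two to differ. A patient whose pain returns may take rescue medication and remain in the study, and with no clinic visit between Weeks 6 and 11 an event normally requires withdrawal between visits. Protocol 3.3 reports mean half-lives of 143 to 197 hours. The 35 days (840 hours) of follow-up therefore span 840/197 = 4.3 to 840/143 = 5.9 half-lives, so the drug washes out during the period the curve covers. That makes some loss of response conceivable but does not measure it.

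At stake is the description of how long response lasts after treatment stops, by arm.

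**Working it through.** The documents state no event count, rate or power for this endpoint, so there is no planned figure to reproduce. The check applies the SAP rule to one patient and then to assumed shares.

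**1. One constructed patient.** Baseline ADPS is 6.0 and Week 6 is 4.0, a change of 100 × (4.0 − 6.0)/6.0 = −33.3%, so the patient is a responder. Weeks 7 to 11 are all 6.0, a change of 0%. The Week 6 visit is on Day 43 (SAP Table 1.2) and the last diary entry on Day 77 (end of Week 11, Table 1.1). The SAP formula is (end date − Week 6 visit date + 1)/7.

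- SAP rule: censored at (77 − 43 + 1)/7 = 5.0 weeks, no event.
- Diary, dating loss at the end of Week 7 (Day 49): (49 − 43 + 1)/7 = 1.0 week.

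**2. Overstatement at Week 11.** Let L be the share of responders who lose the 30% response by Week 11, and q the share of those who leave for lack of efficacy. Assume nobody still responding leaves for that reason and nobody else is censored early. True loss is L and the SAP curve shows Lq, so the overstatement of persistence is L − Lq = L(1−q). All values below are assumptions.

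| L | q | SAP curve shows (Lq) | Overstatement L(1−q) |
|---|---|---|---|
| 60% | 5% | 3% | 57 points |
| 20% | 25% | 5% | 15 points |
| 60% | 25% | 15% | 45 points |
| 80% | 50% | 40% | 40 points |
| any | 100% | L | 0 |
| 0% | any | 0% | 0 |

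A simulated Kaplan-Meier calculation with losses spread over five weeks gave 3.1%, 5.0% and 14.9% for the first three rows, in agreement. If the first two rows were two arms, the arm with more true loss would show less.

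**3. Planned summaries.** SAP 7.6.2.6 reports the 25th percentile, median and 75th percentile. Under the same assumptions these exist only if Lq reaches 25%, 50% and 75%. For L of 20 to 80% and q of 0 to 50%, Lq is at most 40%, so the median is never reached.

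**4. Error of a diary-based rule.** Take as the event two successive weeks with ADPS reduction below 30%. Simulation assumptions: Baseline mean 6.8, SD 0.9, limited to 4.5–9.5; SD of change 2, as in the protocol; mean change −1.5 or −2.5; week-to-week SD 0.3, 0.5 or 0.8; no true change after Week 6. The rule labels 8.1, 13.7 and 22.5% of stable responders as losing response (mean −1.5), or 5.4, 9.0 and 14.5% (mean −2.5).

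Next let true loss be spread evenly over Weeks 7–11, so that 0.8L has occurred by the end of Week 10:

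| L, q | True event-free | SAP rule | Two-week diary rule |
|---|---|---|---|
| 10%, 50% | 92% | 96% (4 points off) | 5–21 points off |
| 20%, 50% | 84% | 92% (8 points off) | 65–79% (5–19 points off) |
| 40%, 25% | 68% | 92% (24 points off) | 53–64% (4–15 points off) |

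The SAP curve reads 92% in the last two rows although true loss doubles from 16% to 32%. The diary rule is the worse of the two when loss is uncommon and diaries are noisy.

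**The case against.** The SAP states its definition openly, with a formula and a censoring rule. Because the protocol leaves the event undefined, the definition contradicts nothing. A reader might infer a departure from the protocol, especially as the summary of changes for Amendment 2 shows superseded text with a pain-based definition. The current protocol carries no such definition, so that reading fails. Nor does any passage say the curve is meant to describe persistence of response; that purpose is inferred from the title and the population.

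The consequence is limited. The endpoint is exploratory, with Kaplan-Meier summaries and no between-group test specified. By-week responder tables (SAP 7.6.5.3 and 7.6.5.4), the Week 6-to-11 cumulative distribution (7.6.5.6) and the diary listings show some return of pain. This stands, but only in part: the tables are not restricted to Week 6 responders, the distribution has no time axis, and none is a time to loss.

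It is also fair to say that a diary rule is not shown to be better. The documents give no relapse or withdrawal rates, and step 4 of the working has cases where the diary rule is further from the truth. This objection stands in full and rules out making a diary version the main one. Retitling alone would cure the mismatch between label and event.

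**Conclusion.** The mismatch is real. Termination for lack of efficacy is the only event, and no current passage in either document adds a pain-score event. The curve therefore describes leaving follow-up, and it overstates persistence of response at Week 11 by about L(1−q) under the two assumptions in step 2 of the working. The overstatement cannot exceed L and is zero if L = 0 or q = 1. Neither quantity is in the documents, so the size is unknown.

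Two stronger readings should be resisted. One is that the curve will be badly wrong or will misorder the arms: that happens only under assumed rates. The other is that the trial's conclusion is at risk: the primary analysis does not use this endpoint. Severity is minor. Calling some outcomes competing risks while censoring them is a wording fault in the same section.

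**What to change.** 1. Retitle the present analysis *time to termination of follow-up for lack of efficacy*.
2. Beside it, with neither ranked as main, add one descriptive Kaplan-Meier version in the same Week 6 responders:
   - Event: the first of two successive evaluable diary weeks (at least 4 entries) with ADPS reduction from Baseline below 30%, or termination for lack of efficacy if earlier.
   - Weeks counted: only Table 1.1 weeks that begin on or after the Week 6 visit date. Those weeks are fixed to Day 1, so with a visit on Day 46, Week 7 (Days 43–49) would include three days before the visit. Skip unevaluable weeks when judging succession.
   - Dating: the event falls at the end of the first such week; censor at the last evaluable week.
   - Rescue: use diary data regardless of rescue, as the primary analysis does, and report the number of rescue users in Weeks 7–11.
3. Replace the competing-risk sentence with a plain statement that those terminations and deaths are censored.

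The cost is SAP wording and a little programming; the diary data are already collected through Week 11. The added version has its own limits. It mislabels some stable responders through weekly noise (about 5–22% under the assumptions in step 4), cannot confirm a loss first seen in Week 11, and leaves patients whose pain is held down by rescue event-free. The two curves should be read together.
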